4. SAMPLE SIZE ESTIMATION

The sample size chosen for this study was selected without statistical considerations. It has been determined adequate to meet the study objectives.

5. SUBJECT RANDOMISATION

Subjects who complete the study screening assessments and meet all the eligibility criteria and are randomised will be assigned a unique randomisation identification number on Day 1 and will receive study products according to the randomisation scheme.

Subjects will be randomized into 1 of 4 sequences (ABCD, BDAC, CADB, and DCBA).

6. ANALYSIS POPULATIONS

[figure not shown]
[figure not shown]
[figure not shown]
Safety Population will include all subjects who have successfully completed eligibility requirements after checking in to the CRU and used at least one study product including subject's OBCC.

Outcomes Population will include a subset of the safety population and will consist of subjects who used a study product and have evaluable PK, subjective effects, or topography data. This population will be used in the summary and analysis of PK, subjective effects, topography, and product use, and all available data will be included in the summary tables to the extent possible.

7. STUDY PRODUCT DESCRIPTIONS

All subjects will use Products A through D

The following products will be tested in this study:

Study Product	Short Description	Long Description
A		████████ HT device with ██████████ American Blend stick
B		████████ HT device with ██████████
C		████████ HT device with ██████████ stick
D	Subjects OBCC	Subject's own brand combustible cigarette (OBCC)

Imperial Brands PLC
Project No. NER01/0004
Celerion Project No. CA35183

8. PHARMACOKINETIC ANALYSIS

8.1 Measurements and Collection Schedule

On each of Days 1, 2, 3 and 4, venous blood samples (~4 mL per sample) for PK analysis of plasma nicotine concentrations will be collected at time 0 (approximately 5 minutes prior to the start of product use) and at 2, 4, 6, 8, 10, 15, 30, 45, 60, 120 and 240 minutes, relative to the start of product use.

8.2 Bioanalytical Method

Plasma nicotine will be analyzed by LC-MS/MS at Celerion Bioanalytical Services Lincoln, Nebraska, using validated analytical methods with appropriate quality controls according to the Food and Drug Administration (FDA) Guidance for Industry (Title 21 CFR Part 58). Additionally, processing of samples will be completed by a non-tobacco user.

8.3 Pharmacokinetic Concentrations

For the concentration tables, unadjusted plasma nicotine concentrations that are BLQ will be set to one-half of the lower limit of quantitation for the calculation of descriptive statistics.

Individual nicotine concentrations will be adjusted for baseline nicotine (“baseline-adjusted”) and all PK parameters will be calculated based on the adjusted concentrations. Baseline adjustment will be performed by subtraction of the pre-existing nicotine concentration from each nicotine concentration obtained after test product administration in that period/day for each subject using the following equation:

$$C_t = C_{t \text{ unadjusted}} - [C_0 \cdot e^{-K_{el} \cdot t_1}]$$

where C_t is the adjusted concentration at time t , $C_{t \text{ unadjusted}}$ is the observed concentration at time t , C_0 is the pre-product use concentration (-5 minutes), $K_{el} = \frac{\ln(2)}{t_{1/2}}$, $t_{1/2}$ is 2 hours (average nicotine half-life), t is the actual sampling time since product administration, and t_1 is the actual sampling time since the time of the pre-product use sample.

After correction for pre-product administration values, some concentrations may be below the limit of quantitation (BLQ) and some may be negative values. Negative values will be assigned a value of zero in the analyses and all other values obtained will be reported as is even if these values are BLQ.

Baseline-adjusted plasma nicotine concentrations will be used for the calculation of the plasma nicotine PK parameters.

Imperial Brands PLC
 Project No. NER01/0004
 Celerion Project No. CA35183

All concentration data will be included in the calculation of the individual PK parameters, the individual concentration-time plots (based on actual sample times), and in the mean concentration-time plots (based on nominal sample times). However, if there are any significant deviations from nominal sample times, some concentration data may be excluded from the descriptive statistics and the mean concentration-time plots and/or additional concentration-time plots of the mean data may be provided. All deviations and excluded data will be listed and discussed in the CSR.

8.4 Noncompartmental Pharmacokinetic Analysis and Parameter Calculation

The appropriate noncompartmental PK parameters will be calculated from the baseline-adjusted plasma nicotine concentration-time data using Phoenix® WinNonlin® Version 8.1 or higher. Actual sample times will be used in the calculations of the PK parameters. The calculation of the actual time for plasma nicotine will be in respect to the start of product use. All PK parameters included in the protocol are listed in [Table 8.1](#) below, and are defined as appropriate for study design.

Table 8.1. Noncompartmental Pharmacokinetic Parameters to be Calculated

Parameter	Label to be Used in the Text, Tables and Figures	Definition	Method of Determination
AUC ₀₋₉₀	AUC0-90	
Area under the baseline-adjusted nicotine concentration-time curve from time zero (defined as the start of the product use session) to the 90-minutes time point.
 
If the 90-minutes plasma concentration is missing, BLQ, or not reportable, then interpolation and/or extrapolation will be conducted, as appropriate. If interpolation and/or extrapolation cannot be reliably performed, then this parameter cannot be calculated.
	Calculated using the Linear Trapezoidal with Linear Interpolation Method

Imperial Brands PLC
 Project No. NER01/0004
 Celerion Project No. CA35183

Parameter	Label to be Used in the Text, Tables and Figures	Definition	Method of Determination
AUC ₀₋₂₄₀	AUC0-240	
Area under the baseline-adjusted nicotine concentration-time curve from time zero (defined as the start of the product use session) to the 240-minutes time point.
 
If the 240-minutes plasma concentration is missing, BLQ, or not reportable, then interpolation and/or extrapolation will be conducted, as appropriate. If interpolation and/or extrapolation cannot be reliably performed, then this parameter cannot be calculated.
	Calculated using the Linear Trapezoidal with Linear Interpolation Method
AUC _t	AU Ct	Area under the baseline-adjusted nicotine concentration-time curve from time zero (defined as the start of the product use session) to the time of the last measurable non-zero concentration.	Calculated using the Linear Trapezoidal with Linear Interpolation Method
AUC _{inf}	AUCinf	Area under the baseline-adjusted concentration-time curve from time 0 extrapolated to infinity	Calculated as: AUC _t + (C _{last} /K _{el}) where C _{last} is the last observed/measured concentration
AUC% _{extrap}	AUC% _{extrap}	Percent of AUC _{inf} extrapolated to infinity	Calculated as: (1 – AUC _t /AUC _{inf}) x 100
C _{max}	Cmax	Maximum baseline-adjusted plasma concentration over the duration of the measurement interval.	Taken directly from bioanalytical data
C _{last}	Clast	Plasma baseline-adjusted nicotine concentration at last time point measured.	Taken directly from bioanalytical data
T _{max}	T _{max}	Time to reach the maximum baseline-adjusted plasma concentration. If the maximum value occurs at more than one time point, T _{max} is defined as the first time point with this value	Taken from clinical database as the difference in the time of administration and the time of the blood draw which is associated with the C _{max}

Imperial Brands PLC
 Project No. NER01/0004
 Celerion Project No. CA35183

Parameter	Label to be Used in the Text, Tables and Figures	Definition	Method of Determination
$T_{1/2}$	$T_{1/2}$	Apparent first-order terminal elimination half-life.	Calculated as $\ln 2/K_{el}$
K_{el}	K_{el}	Apparent first-order terminal elimination rate constant	Calculated by linear least-squares regression analysis using the maximum number of points in the terminal log-linear period (e.g., three or more non-zero plasma concentrations).

Pharmacokinetic parameters will not be calculated for subjects with less than 3 consecutive post-product administration time points with quantifiable concentrations. Subjects for whom there are insufficient data to calculate the PK parameters will be included in the concentration tables only and excluded from the summary statistics, statistical analysis, and mean profiles.

The K_{el} will be determined using linear regressions composed of least 3 data points. The K_{el} will not be calculated if 1) the terminal elimination phase is not apparent, 2) if C_{max} is one of the 3 last data points, or 3) if the R^2 value is less than 0.75. In cases where the K_{el} interval is not calculated, the values of $T_{1/2}$ will not be reported.

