7.3.1.1 Analysis of Variance

A linear mixed model for analysis of variance will be performed on the log-transformed PK parameters C_{max} and AUC following the morning product use session on each of Days 1, 2, 3, and 4. The model will include sequence, study product, and study day as fixed effects and subject-nested-within-sequence as a random effect. Sequence will be tested using subject-nested-within-sequence as the error term. Geometric least-squares means (LSM) and 95% confidence intervals (CIs) will be provided for the PK parameters of C_{max} and AUC by study product. Geometric LSM ratio, 95% CIs of geometric LSM ratio, and p-values will be provided for the study product comparisons in C_{max} and AUC. The comparisons of interest will include each of the study products compared to each other.

The above statistical analyses will be performed using the appropriate SAS procedure.

Non-parametric analysis (Wilcoxon Signed Rank test) will be performed for the comparisons of T_{max} .

Details of the statistical methods will be provided in the SAP.

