8.5 Data Summarization and Presentation

SAS® software (Version 9.4) will be used for all data presentation and summarization including statistical analyses, summary tables, graphs, and data listings. Descriptive statistics will be generated for plasma concentrations and PK parameters.

The plasma nicotine concentrations will be listed for all subjects and presented with the same level of precision as received from the bioanalytical laboratory. Plasma nicotine concentrations will be summarised by study product for all subjects in the outcomes population, by sex and overall using descriptive statistics. Summary statistics, including sample size (n), arithmetic mean (mean), standard deviation (SD), coefficient of variation (CV%), standard error of the mean (SEM), minimum, median, and maximum will be calculated for all nominal time point for both baseline-adjusted and unadjusted concentrations. Excluded subjects or timepoints will be included in the concentration tables, but will be excluded from the summary statistics and noted as such in the tables. All BLQ values will be presented as “BLQ” in the concentration tables and footnoted accordingly.

Imperial Brands PLC
 Project No. NER01/0004
 Celerion Project No. CA35183

Mean and individual concentration-time profiles will be presented on linear and semi-log scales. Linear mean plots will be presented with and without SD.

Plasma nicotine PK parameters will be listed and summarised by product (overall and by sex) for all subjects in the Outcomes Population. Pharmacokinetic parameters will be reported to 3 significant figures for individual parameters, with the exception of T_{max} , which will be presented with 2 decimal places. Summary statistics will be reported, including n, mean, SD, CV%, SEM, minimum, median, and maximum by study product (overall and by sex). In addition, geometric mean (geom mean) and geometric CV% (geom CV%) will be provided for the C_{max} and AUC parameters by study product (overall and by sex).

Excluded subjects or timepoints will be listed in the PK parameter tables, but will be excluded from the summary statistics and noted as such in the tables.

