8.6 Statistical Analysis of PK Parameters

A linear mixed model for analysis of variance (ANOVA) will be performed on the natural log-transformed PK parameters C_{max} and AUC_t following the morning product use session on each of Days 1, 2, 3, and 4. The model will include sequence, product, and study period as fixed effects and subject-nested-within-sequence as a random effect. Sequence will be tested using subject-nested-within-sequence as the error term for inferential purposes. Geometric least-squares means (LSM) and 95% confidence intervals (CIs) will be provided for the PK parameters of C_{max} and AUC_t by product. Geometric LSM ratio, 95% CIs of geometric LSM ratio, and p-values will be provided for the product comparisons in C_{max} and AUC_t . The comparisons of interest will include each of the products compared to each other.

The above statistical analyses will be performed using the following SAS[®] code:

```
Proc mixed data=<>;
class subject sequence period product;
model log(parameter) = sequence period product / ddfm=KR;
random subject (sequence);
lsmeans product/diff cl alpha=0.05;
estimate "Product A versus Product D" Product 1 0 0 -1/cl alpha=0.05;
estimate "Product B versus Product D" Product 0 1 0 -1/cl alpha=0.05;
```

Imperial Brands PLC
 Project No. NER01/0004
 Celerion Project No. CA35183

estimate “Product C versus Product D” Product 0 0 1 -1/cl alpha=0.05;
 estimate “Product A versus Product B” Product 1 -1 0 0/cl alpha=0.05;
 estimate “Product A versus Product C” Product 1 0 -1 0/cl alpha=0.05;
 estimate “Product B versus Product C” Product 0 1 -1 0/cl alpha=0.05;
 run;

Note: Protocol defined the study as Days 1-4 and the CRF had periods 1-4 (each have one day), respectively. Period will be used in the database and therefore in the statistical analysis.

Non-parametric analysis (Wilcoxon Signed Rank test) will be performed for the comparisons of T_{max} between each of the study products. Median difference and 95% CI of the difference will be presented for each comparison. The CI is constructed using Walsh Averages and the appropriate quantile of the Wilcoxon Signed Rank Test Statistic.

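### Does the primary AUCt need a rule for a missing 240-minute sample, or a companion model on AUC0-240?

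*SAP*

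**What the plan says.** Four parts of the SAP bear on this.

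- **Definition (8.4, Table 8.1).** AUCt runs "to the time of the last measurable non-zero concentration". For AUC0-240 the table adds: "If the 240-minutes plasma concentration is missing, BLQ, or not reportable, then interpolation and/or extrapolation will be conducted, as appropriate". If that cannot be done reliably, AUC0-240 is not calculated.
- **Data used (8.3 to 8.5).** "All concentration data will be included in the calculation of the individual PK parameters". The floor is in 8.4: "Pharmacokinetic parameters will not be calculated for subjects with less than 3 consecutive post-product administration time points with quantifiable concentrations". Section 8.5 rules out imputation. The last two scheduled draws are at 120 and 240 minutes (8.1).
- **Model (8.6).** The mixed model "will be performed on the natural log-transformed PK parameters" Cmax and AUCt, the two parameters named in the primary objective (Protocol 2.1, SAP 2.1). Protocol 7.3.1.1 refers to AUC without a suffix.
- **Reporting (8.5 and the table shells).** AUCt, AUC0-240 and the extrapolated percentage are listed by subject. For Cmax and the AUCs, "geometric mean (geom mean) and geometric CV% (geom CV%) will be provided" by product. The concentration tables mark missing values by subject. No product ratio or interval is planned for AUC0-240.

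**The concern.** Two neighbouring rows of one table look unevenly specified, and the row with less detail is the primary one. Read together, the provisions shorten a profile with no usable 240-minute value and keep it in the analysis. A within-subject ratio could then compare, say, 0-120 minutes of one product with 0-240 minutes of another. The affected product would look lower for a reason unrelated to nicotine delivery.

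The fixed-window measure that would show this is already computed but is not modelled. The primary results table does not say how many profiles end early. Adding AUC0-240 to the same model looks like a cheap safeguard for a primary result.

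**Working it through.** **Is the handling undefined?** No. AUC0-240 ends at a fixed clock time, so it needs an instruction when nothing usable was measured then. AUCt ends wherever the last measurable non-zero value lies, so a missing 240-minute sample moves its end to the previous such value, normally 120 minutes. With imputation barred, only one result is possible. Cmax, the other primary parameter, hardly depends on the last draw.

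**Effect on one profile.** The documents give no concentrations and no missing-sample rate, so these inputs are assumptions:

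- the SAP sampling times and the linear trapezoid;
- a linear rise to a peak at 6 or 8 minutes, then a biexponential fall;
- slow fraction 0.3-0.6, fast half-life 8-20 minutes, terminal half-life 90, 120 or 150 minutes (the baseline adjustment in SAP 8.3 uses 2 hours).

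Central case (peak 1 at 6 minutes, slow fraction 0.4, fast half-life 12, terminal half-life 120): C120 = 0.208 and C240 = 0.104.

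- Last trapezoid = 120 × (0.208 + 0.104)/2 = 18.7.
- AUC0-240 = 66.4, so the share lost is 18.7/66.4 = 28%.
- Over all 72 profiles the share runs from 19.4% to 35.4%.

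**Effect on a product's geometric mean.** With k of 24 profiles short by share s on that product only, the shift is (1 − s)^(k/24) − 1.

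| s | k = 1 | k = 3 |
|---|---|---|
| 0.194 | −0.9% | −2.7% |
| 0.282 | −1.4% | −4.1% |
| 0.354 | −1.8% | −5.3% |

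For scale, the design leaves 96 − 24 − 3 − 3 = 66 residual degrees of freedom. The lower 95% limit of a ratio lies exp(−t × SD × √(2/24)) − 1 from the estimate. At assumed within-subject CVs of 20, 30 and 40% that is −10.8%, −15.6% and −19.9%.

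**Effect on the interval.** The four planned sequences were simulated with six subjects each, 20,000 runs per cell, the three shares above and the three CVs.

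| Loss of 240-minute samples | Coverage of 95% interval | Bias in mean ratio | Rise in residual SD |
|---|---|---|---|
| Random, 1% | 94.7-95.3% over the three random rates | at most 0.15% over the three random rates | 0.2-2.5% |
| Random, 2% | as above | as above | 0.4-4.7% |
| Random, 5% | as above | as above | 0.8-11% |
| Exactly 3 of 24, all on one product | 87-94% | −2.7% to −5.3% | not computed |

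At 28% loss, a 2% rate and CV 30%, the residual SD rises 1.2%, which moves the lower limit from −15.6% to −15.7%.

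The last row needs three losses on one product and none on the others. The binomial chance of three or more on a given product of 24 is 0.2%, 1.2% and 12% at rates of 1, 2 and 5%.

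**Are losses likely to differ by product?** Subjects are confined throughout, and the ad libitum session starts only after the 4-hour draw (Protocol 3.1, 3.2). Nothing in the schedule links a lost sample to a product.

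**The case for a change.** The best argument for acting is that no sample need be lost. SAP 8.3 sets negative adjusted values to zero, and a zero at 240 minutes also ends AUCt early. This is more likely with a product that delivers less nicotine, so it would not be random. On the same profiles AUCt would then lie 15-26% below AUC0-240.

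The route is real but narrow. The amount subtracted at 240 minutes is the pre-use value × 2^(−245/120) = 0.243 of that value. A zero therefore requires the observed 240-minute concentration to be below about 24% of the pre-use value.

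- If a subject's own half-life is 2 hours or more, the pre-use residue alone keeps the observed value at or above that level, apart from assay error.
- At a 90-minute half-life the residue is 2^(−245/90) = 0.152, so the product's own contribution must be under 0.243 − 0.152 = 0.091 of the pre-use value. In the central 90-minute profile that contribution is 0.066 of its peak, so the pre-use value would have to exceed 0.066/0.091 = 0.73 of that peak. At least 12 hours of abstinence precede each session.

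The documents give no frequency for such zeros, so the route cannot be excluded, but no effect has been shown.

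It is also true that the primary table has no count of short profiles, that the protocol words the AUCt end point in several ways, and that an AUC0-240 model would be one more procedure call. That model has its own difficulty. The AUC0-240 rule is also triggered by values below the limit of quantitation, while SAP 8.3 keeps adjusted values of that kind as they are. Observed low values could therefore be replaced by extrapolation under a method left to discretion, and profiles judged unreliable would drop out. It would also add six more comparisons.

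**Conclusion.** No change to the plan. The difference between the two rows reflects two kinds of parameter, one with a floating end and one with a fixed end. The SAP's naming of AUCt where the protocol's model section says only AUC agrees with the primary objective.

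Under random loss at 1-5% the planned interval keeps its nominal coverage and the ratio is essentially unbiased. The cost is a residual SD higher by 0.2-11%, with the top of that range at 5% loss, 20% CV and the largest area share. With all 240-minute values present and non-zero the effect is nil, and an AUC0-240 model would duplicate the AUCt result.

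These sizes rest on assumed profiles, CVs and loss rates, and on losses being unrelated to product. If short profiles do occur, the by-subject concentration and parameter tables identify them. Whoever writes the report can count them, and can form a paired AUC0-240 ratio from the listed values, without any new provision.

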8.5 Data Summarization and Presentation

SAS® software (Version 9.4) will be used for all data presentation and summarization including statistical analyses, summary tables, graphs, and data listings. Descriptive statistics will be generated for plasma concentrations and PK parameters.

The plasma nicotine concentrations will be listed for all subjects and presented with the same level of precision as received from the bioanalytical laboratory. Plasma nicotine concentrations will be summarised by study product for all subjects in the outcomes population, by sex and overall using descriptive statistics. Summary statistics, including sample size (n), arithmetic mean (mean), standard deviation (SD), coefficient of variation (CV%), standard error of the mean (SEM), minimum, median, and maximum will be calculated for all nominal time point for both baseline-adjusted and unadjusted concentrations. Excluded subjects or timepoints will be included in the concentration tables, but will be excluded from the summary statistics and noted as such in the tables. All BLQ values will be presented as “BLQ” in the concentration tables and footnoted accordingly.

Imperial Brands PLC
 Project No. NER01/0004
 Celerion Project No. CA35183

Mean and individual concentration-time profiles will be presented on linear and semi-log scales. Linear mean plots will be presented with and without SD.

Plasma nicotine PK parameters will be listed and summarised by product (overall and by sex) for all subjects in the Outcomes Population. Pharmacokinetic parameters will be reported to 3 significant figures for individual parameters, with the exception of T_{max} , which will be presented with 2 decimal places. Summary statistics will be reported, including n, mean, SD, CV%, SEM, minimum, median, and maximum by study product (overall and by sex). In addition, geometric mean (geom mean) and geometric CV% (geom CV%) will be provided for the C_{max} and AUC parameters by study product (overall and by sex).

Excluded subjects or timepoints will be listed in the PK parameter tables, but will be excluded from the summary statistics and noted as such in the tables.

The level of precision for each concentration and PK parameter statistic will be presented as follows: minimum/maximum in same precision as in the bioanalytical data (concentrations) or as mentioned above for the PK parameters, mean/median/geom mean in one more level of precision than minimum/maximum, SD/SEM in one more level of precision than mean/median, n will be presented as an integer, CV% and geom CV% will be presented to the nearest tenth.

Missing data will be treated as missing and no data imputation will be conducted.

